We propose a pre/posttest, RCT with a 4-step (12 months per step), stepped-wedge design³ to compare effects of usual outpatient palliative care (usual care) and usual care along with either nurse-led or chaplain-led DT on patient outcomes (dignity impact, existential tasks [preparation for death, life completion], cancer prognosis awareness [peaceful awareness, treatment preferences]). We will assign 6 outpatient palliative care sites to usual care during the first-step, and randomly assign two sites per step to begin and continue DT led by either a nurse or a chaplain during each of the next 3 steps. During the usual care steps, 280 patients will complete pretest measures (patient outcomes, covariates [physical symptoms, spiritual distress], and satisfaction with palliative spiritual care services), receive usual palliative care, and complete posttest measures (patient outcomes, covariates, satisfaction). During the experimental steps as part of routine palliative care service delivery, 280 patients will complete pretest measures, receive nurse-led or chaplain-led DT, and complete posttest measures. Using mixed level analysis with site, provider (nurse, chaplain) and time (step) included in the model, we will compare the usual care and each of the DT groups for effects on dignity impact, existential tasks, and cancer prognosis awareness and explore the moderating effects of physical symptoms and spiritual distress. We will also determine the effect of usual care and DT on the patient's satisfaction with palliative spiritual care services and the report of the patient's unmet spiritual needs.

Specific Aims:

In a diverse sample of 560 elderly cancer patients, the specific aims are to:

Aim 1. Compare usual care and usual care with nurse-led or chaplain-led DT groups for effects on:

a) patient outcomes (dignity impact, existential tasks [preparation for death, life completion], cancer prognosis [peaceful awareness, treatment preferences]). We hypothesize that, controlling for pretest scores, each of the DT groups will have higher scores on the dignity impact (1° outcome) and existential tasks (2° outcome) measures than the usual care group. Also patients in each of the DT groups will report better peaceful awareness and treatment preferences more consistent with their cancer prognosis (2° outcomes) than the usual care group; and

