b) processes of delivering palliative spiritual care services (satisfaction and unmet spiritual needs; 2° outcomes). We hypothesize that each of the DT groups will show increased patient satisfaction with spiritual care services and fewer unmet spiritual needs compared to the usual care group.

Aim 2. Explore the influence of physical symptoms and spiritual distress on the dignity impact and existential tasks effects of usual palliative care and nurse-led or chaplain-led DT. We hypothesize that physical symptoms and spiritual distress will significantly affect intervention effects. This rigorous trial of DT will constitute a landmark step in gero-oncology palliative care and spiritual health services research.

Study design:

We propose a 6-site, pre/posttest, randomized, controlled 4-step, stepped-wedge design to compare the effects of usual outpatient palliative care and usual outpatient

palliative care along with nurse-led or chaplain-led DT on patient outcomes and palliative care processes. We will assign the 6 sites to usual care during the first-step period (10 months), and randomly assign 2 sites per step to begin and continue DT during each of the next 3 steps (10 months each).

Figure 1 shows the stepped-wedge study design with projected numbers of

completed patients needed per site, step period, and group (usual care, DT led by either a nurse or a chaplain). [name], a highly qualified statistician will conduct the randomization of site to steps 2-4. Each step will be 10 months long, with DT training during a 1-week period between steps. For each site/step, a quota of 50% of the participants will report low or high distress on the Personal Dignity Inventory to assure we recruit a sample with a range of problems threatening their dignity. Each patient will participate for 4-6 weeks. Over the 10 months at each step, we expect 23-24 patients to participate at each site (93-94 total patients per site).

Figure 1. Stepped-wedge design	N per step per site			Total N
Site 6	23	23	23	24 93
Site 5	23	23	23	24 93
Site 4	24	23	23	24 94
Site 3	24	23	23	24 94
Site 2	24	23	23	23 93
Site 1	24	23	23	23 93
Step	1	2	3	4
Patients/				
Step Period	142	138	138	142 560
Usual Care				280
Nurse-Led DT				140
Chaplain-Led DT				140
Step Period Duration (mo)	10	10	10	10 40

Subject identification, recruitment and consent:

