Aim 1. Linear mixed effects models will be used to compare the effects of usual palliative care with usual palliative care with nurse-led and chaplain-led DT groups on (a) patient outcomes and (b) processes of delivering palliative spiritual care services. Random effects terms will be used to model the variations between sites. A main challenge of data analysis of a stepped-wedge design is the modeling of potential time trends. We plan to treat time as a continuous variable and utilize smoothing splines to model potential time trends. Smoothing splines is a nonparametric method that allows flexibility to model different time trends without overfitting by enforcing a smoothness constraint. Likelihood ratio tests will be used to determine the statistical significance of the intervention effect on various outcome measures. We hypothesize that, controlling for pretest scores, patients in both nurse-led and chaplain-led DT groups will have higher dignity impact scores, higher preparation for death and life completion scores, better peaceful awareness, and treatment preferences more consistent with their cancer prognosis than the usual care groups. We also expect the patients in the DT groups to be more satisfied with the palliative care and have fewer unmet spiritual needs than the usual care groups. We do not expect significant difference between nurse-led and chaplain-led DT interventions. Note that, this does not necessarily mean that the two interventions are equally effective. We do not seek to test the equivalence of the two intervention arms. At this point, it is premature to speculate on their relative efficacy. We expect most patients in this study to have metastatic cancer. If a sizable portion of our sample has non-metastatic cancer, we will explore if they respond to DT differently than those with metastatic disease.

Aim 2. The effect of physical symptoms and spiritual distress on the dignity impact and existential tasks will be modeled nonparametrically using smoothing splines. Our models will include both main effect for physical symptoms and spiritual distress and their interactions with the intervention. This analysis will provide insight on the type of patients most in need of and most likely to benefit from the DT intervention. Likelihood ratio tests will be used to determine the significance of the interaction. We hypothesize that patients' levels of spiritual distress and physical symptom scores will moderate the intervention effect.

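### Pretest adjustment is stated for the Aim 1(a) outcomes but not for satisfaction with spiritual care (Aim 1b), although satisfaction is measured at pretest; stating it would gain precision at almost no cost

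*Combined protocol and SAP*

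**What the plan says.** Under Specific Aims, the Aim 1(a) hypothesis carries the adjustment: "We hypothesize that, controlling for pretest scores, each of the DT groups will have higher scores on the dignity impact (1° outcome". Data analysis, Aim 1, repeats it for the patient outcomes: "We hypothesize that, controlling for pretest scores, patients in both nurse-led and chaplain-led DT groups will have higher dignity impact scores". These are the only two places where control for pretest is mentioned.

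The Aim 1(b) hypothesis appears in the same two sections, both times without it. Specific Aims states: "each of the DT groups will show increased patient satisfaction with spiritual care services and fewer unmet spiritual needs compared to the usual care group". Data analysis says "We also expect the patients in the DT groups to be more satisfied with the palliative care and have fewer unmet spiritual needs", directly after the sentence that has the adjustment.

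Satisfaction is measured at both times. The design paragraph in Background and Purpose says that in the usual care steps "280 patients will complete pretest measures (patient outcomes, covariates [physical symptoms, spiritual distress], and satisfaction with palliative spiritual care services", and that the same patients later "complete posttest measures (patient outcomes, covariates, satisfaction". Unmet spiritual needs does not appear in the pretest list.

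The lists of model terms do not supply the missing covariate. Background and Purpose names site, provider and time. Data analysis, Aim 1, names random site effects and a smoothing spline for time, in one model statement that covers both parts of Aim 1. Data analysis, Aim 2, says "Our models will include both main effect for physical symptoms and spiritual distress and their interactions with the intervention".

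**The concern.** A pretest value of the outcome is often the strongest available predictor of its posttest value. The plan uses it for dignity impact and the other patient outcomes, and gives no reason for treating satisfaction differently. An analyst who follows the wording would compare posttest satisfaction alone and leave in variance that data already in the database could remove.

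The design adds a second reason. Only six sites are randomised, and patients are recruited after their site's condition is set. Under Study Procedures, the research assistant who recruits and consents patients also tells the nurse or chaplain that the patient is available for usual care or DT, depending on site and step. Patients entering after a switch could therefore differ at pretest. The recruitment quota balances dignity-related and spiritual distress, not satisfaction. The imbalance check in Data analysis is descriptive, with no adjustment tied to it.

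Silence also leaves the choice between an adjusted and an unadjusted analysis open until after the data are seen.

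**Working it through.** **1. What can be reproduced.** The plan gives no power, detectable effect, SD, ICC or pretest-posttest correlation, so only its sample layout can be checked. Figure 1 step totals are 142 + 138 + 138 + 142 = 560. Usual care is all six sites in step 1 (142), four sites in step 2 (4 × 23 = 92) and two in step 3 (2 × 23 = 46), and 142 + 92 + 46 = 280. That leaves 280 for DT. If one nurse-led and one chaplain-led site switch at each step, each provider has 69 + 47 + 24 = 140. All of this agrees with the plan.

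**2. Assumptions, not from the documents.** Pretest-posttest correlation rho = 0.3, 0.5, 0.7; site ICC = 0.01, 0.05, 0.10; one nurse-led and one chaplain-led site per switch; total SD = 1; two-sided 5% tests (the plan gives 0.05 without sidedness); pretest reduces within-site variance only.

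**3. Simple check, ignoring clustering.** Adjustment multiplies variance by 1 − rho², a cut of 9%, 25% or 49%. For one DT group against usual care (140 v 280), the difference detectable with 80% power is (1.960 + 0.842) × √(1/280 + 1/140) = 2.802 × 0.1035 = 0.290 SD. Multiplying by √(1 − rho²) gives 0.277, 0.251 and 0.207 SD.

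**4. Stepped-wedge model.** Generalised least squares on the 24 site-by-step cell means of Figure 1, with step effects, one effect per provider and a random site intercept. The variance of a cell mean is ICC + (1 − ICC)(1 − rho²)/n, and two cells of the same site have covariance ICC. The SE of one DT-versus-usual-care contrast, in SD units, with the variance cut in brackets:

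| ICC | Unadjusted | rho 0.3 | rho 0.5 | rho 0.7 |
|---|---|---|---|---|
| 0.01 | 0.157 | 0.151 (8%) | 0.138 (22%) | 0.117 (44%) |
| 0.05 | 0.170 | 0.163 (8%) | 0.149 (23%) | 0.125 (46%) |
| 0.10 | 0.170 | 0.163 (9%) | 0.149 (24%) | 0.123 (47%) |

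A linear time trend in place of step effects gave the same values. The planned spline was not modelled.

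**5. In terms of power.** Power is approximately Φ(d/SE − 1.96). At ICC 0.05 and rho 0.5:
- d = 0.4 SD: 0.4/0.170 = 2.35 gives 65%; 0.4/0.149 = 2.68 gives 77%. Gain about 12 points.
- d = 0.6 SD: 0.6/0.170 = 3.53 gives 94%; 0.6/0.149 = 4.03 gives 98%. Gain about 4 points.

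The power gain depends heavily on the assumed effect, so the variance reduction is the safer summary.

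**6. Imbalance.** A pretest difference of δ SD between DT and usual-care patients, net of site and time, would leave about rho × δ in an unadjusted estimate. For illustration, 0.5 × 0.2 = 0.10 SD. Nothing in the documents indicates what δ would be.

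**The case against.** The strongest reply is that the plan is silent on this point and does not exclude adjustment. One model statement covers both parts of Aim 1 and lists no covariates for either. The pretest phrase sits in a hypothesis sentence, not in a model specification, and the satisfaction sentence follows as a continuation. In a design labelled pre/posttest, with satisfaction measured twice, adjustment may well be intended throughout. This stands. A reader might infer that the plan has decided on an unadjusted satisfaction analysis; the text does not show that.

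A reader might also infer that the Aim 2 models omit the pretest outcome. That does not follow. The Aim 2 paragraph does not restate site or time either, and nobody would conclude that those are dropped. If they carry over from Aim 1, so most naturally does the pretest score, since dignity impact and existential tasks are Aim 1(a) outcomes.

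On size, every input beyond the Figure 1 counts is assumed. A low correlation for satisfaction is plausible: pretest comes before that day's nurse or chaplain care, so some patients may rate spiritual care they have barely received. At rho 0.3 the variance cut is only 8% to 9%. On bias, the distress quota, site effects and time trend give some protection against drift in case mix, although none of them balances satisfaction itself.

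What survives is narrower: no model statement provides the covariate for satisfaction, the wording attaches it to other outcomes only, and the data to include it are already collected.

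**Conclusion.** The point holds as a nearly free improvement, mainly for one secondary outcome. Read literally, the satisfaction comparison is posttest-only and less precise than it need be. Under rho 0.3 to 0.7 and ICC 0.01 to 0.10, pretest adjustment would reduce the variance of each DT-versus-usual-care contrast by roughly 8% to 47%. The documents do not fix where in that range the trial would fall.

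A claim that the reported satisfaction effect will be biased would go too far: imbalance is possible with six randomised sites and recruitment after allocation is known, but none is shown. The primary outcome, dignity impact, is not affected, because its hypothesis already carries the adjustment. Unmet spiritual needs is affected only if a pretest value exists, and none is listed. For Aim 2 the issue is clarity of specification, with no established loss.

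**What to change.** In Data analysis, Aim 1, add to the model specification: posttest satisfaction with spiritual care will be analysed in the same linear mixed model as the Aim 1(a) outcomes, with the patient's pretest satisfaction score as a covariate; unmet spiritual needs will be treated likewise only if a pretest value is collected. Reword the Aim 1(b) hypothesis under Specific Aims to match.

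As a clarification, add to Data analysis, Aim 2, that the moderator models carry over the site, time and pretest-outcome terms of Aim 1.

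The cost is a few sentences of analysis text and one degree of freedom per model, with no new data, visits or staff. The wording should be settled before the outcome data are analysed.

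### Aim 2 names no moderator-by-time term, so about 56% of any linear drift over the steps in the moderator-outcome slope would appear as moderation of DT

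*Combined protocol and SAP*

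**What the plan says.** Data analysis, Aim 2, sets the form of the moderators: "The effect of physical symptoms and spiritual distress on the dignity impact and existential tasks will be modeled nonparametrically using smoothing splines". It then lists the terms, "Our models will include both main effect for physical symptoms and spiritual distress and their interactions with the intervention", and the test, "Likelihood ratio tests will be used to determine the significance of the interaction". The significance level given at the start of Data analysis is 0.05.

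Time is dealt with under Aim 1, which says "A main challenge of data analysis of a stepped-wedge design is the modeling of potential time trends" and continues "We plan to treat time as a continuous variable and utilize smoothing splines to model potential time trends". Site is covered by "Random effects terms will be used to model the variations between sites". Background and Purpose describes the model for both the group comparison and the moderation question as "Using mixed level analysis with site, provider (nurse, chaplain) and time (step) included in the model". So a time trend in the outcome is planned, and it is reasonable to read it as carried into Aim 2. Nothing in the documents lets the relation between a moderator and the outcome change over calendar time, in a main model or a sensitivity analysis.

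Study design puts all six sites on usual care in step 1 and will "randomly assign 2 sites per step to begin and continue DT during each of the next 3 steps".

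Aim 2 is worded as exploratory. It also carries a hypothesis that the moderators will matter and a significance test, and its stated purpose is to identify the patients who need DT most and gain most from it.

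**The concern.** In a stepped wedge, treatment and calendar time are correlated by construction. A time main effect removes a drift in the level of the outcome, which is what the DT main effect needs. It does not remove a drift in a slope. Suppose the association between symptoms (or spiritual distress) and dignity impact strengthens or weakens over the trial for reasons unrelated to DT. The only listed term that can take up that change is moderator-by-DT. A secular change could then be read as guidance on which patients to select for DT.

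Randomising sites to steps does not help. In Figure 1 every site has 23 patients in steps 2 and 3, so every permitted allocation gives the same numbers of DT and usual-care patients at each step. The distress quota in Exclusion criteria balances levels of distress by site and step, not slopes. The same is true of the planned check of patient characteristics over time.

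**Working it through.** **Inputs.** Figure 1 cell counts (23-24 per site and step; step totals 142, 138, 138, 142) and the rollout come from Study design. The level of 0.05 comes from Data analysis; two-sided testing is assumed. The documents give no SD, moderator slope or drift, so outcome residual and moderator are put in SD units and drift is shown as a range.

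**1. Reproduce the plan's totals.** DT patients by step: 0, 46, 92, 142, total 280. Usual care: 142, 92, 46, 0, total 280. Both match Figure 1.

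**2. Link between DT and time.**
- Mean step, DT: (46×2 + 92×3 + 142×4)/280 = 936/280 = 3.343.
- Mean step, usual care: (142×1 + 92×2 + 46×3)/280 = 464/280 = 1.657.
- Gap: 1.686 steps, or 1.686/3 = 56.2% of the range from step 1 to step 4.
- Variance of step: (284×2.25 + 276×0.25)/560 = 1.264, SD 1.124. Correlation: (1.686×0.25)/(0.5×1.124) = 0.75. R² = 0.562.

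**3. Share of a drift that loads on moderator-by-DT.** Take a moderator with the same distribution in every site-step cell and a slope that changes by f(step). Under the listed terms the interaction is biased by mean f among DT patients minus mean f among usual-care patients.

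| Change in slope | Calculation | Share |
|---|---|---|
| Linear, as share of first-to-last change | 1.686/3 | 56% |
| Sustained from step 2 | 280/280 − 138/280 | 51% |
| Sustained from step 3 | 234/280 − 46/280 | 67% |
| Step 4 only | 142/280 − 0 | 51% |
| Step 3 only | 92/280 − 46/280 | 16% |
| Step 2 only | 46/280 − 92/280 | −16% |
| Symmetric (steps 1 and 4) | 142/280 − 142/280 | 0% |

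**4. False-positive rate with no true moderation.** SE of the interaction = 1/√(560×0.25) = 0.0845. For linear drift d per step, bias b = 1.686d and rejection = Φ(b/SE − 1.96) + Φ(−b/SE − 1.96).

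| d (SD per step) | b | Rejection by formula | Simulated |
|---|---|---|---|
| 0 | 0 | 5.0% | 5.2% |
| 0.01 | 0.017 | 5.5% | – |
| 0.02 | 0.034 | 6.8% | – |
| 0.03 | 0.051 | 9.2% | 8.6% |
| 0.05 | 0.084 | 16.9% | 17.4% |
| 0.10 | 0.169 | 51.4% | 50.0% |

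The simulations used the Figure 1 layout, fixed site and step effects, a linear moderator and one DT contrast, with 2,000 trials per setting (2,500 at d = 0.03). A 50/50 low/high moderator gave 49.8% at d = 0.10.

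**5. With moderator-by-time added.** Simulated rejection is 4.4-5.7% in every setting tried. Linear time is enough because the DT share by step is 0, 1/3, 2/3, 1. DT adjusted for linear step is therefore uncorrelated with any function of step.

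**6. Price.** Variance inflation = 1/(1 − 0.562) = 2.28. SE = 0.0845×√2.28 = 0.128, about 50% larger. Effective N = 560/2.28, about 245. The interaction detectable with 80% power in the listed model is 0.0845×2.80 = 0.237. In the adjusted model its power is Φ(0.237/0.1277 − 1.96), about 46%.

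**The case against.** The strongest reply is that the harm is hypothetical. Nothing in the documents shows that the slopes drift. Without drift the planned test keeps its level, and up to 0.02 SD per step it stays close to it. The 50% figure needs a total slope change of 0.30 SD from step 1 to step 4. This stands. Some features of the trial make exactly zero drift a strong assumption: 4.5 years of data collection, palliative services still being developed at one site, and contact either in person or by video. They do not show that drift exists.

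The percentages also come from a simpler model than the planned one, which has splines in the moderators, random site effects, continuous time, pretest adjustment and two DT groups. That stands too. The percentages are illustrative, though the omitted-term argument does not depend on the moderator being linear.

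A reader might infer that any calendar drift becomes DT moderation. Step 3 of the working shows otherwise: the share runs from zero to about two-thirds, depending on shape.

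A reader of the Aim 2 paragraph alone might infer that time is left out of the moderation model. Background and Purpose places site, provider and time in it. The gap is one unnamed interaction, so it is under-specification rather than neglect of time.

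Finally, in an exploratory aim the adjusted model exchanges a possible bias for a certain loss of precision. This is a fair reason not to make it the sole analysis.

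**Conclusion.** The point holds in a conditional form. The Aim 2 terms leave moderator-by-DT open to secular change in the moderator-outcome slope, and the rollout fixes how much of it gets through: about 56% of a linear change and 51-67% of a sustained one. These shares follow from Figure 1 and assume only that the moderator is similarly distributed across site-step cells. The error rates rest in addition on assumed drift sizes and the simplified model.

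The documents do not support saying that the Aim 2 result will be biased, or that its error rate is inflated as a matter of fact. They support saying that the plan as written could not tell DT moderation from drift. The consequence is confined to an exploratory aim. The primary outcome and the Aim 1 comparison are not touched. It is a cheap improvement worth making, not a flaw that undermines the trial.

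**What to change.** In Data analysis, Aim 2, prespecify a second model for each outcome. It keeps the Aim 1 terms (site random effect, time, pretest score) and adds a moderator-by-time interaction for each moderator, linear in time. Report the moderator-by-DT estimate and test from both models side by side. State beforehand that DT moderation will be described as robust only if the adjusted estimate supports it, and that a signal seen only in the listed model will be reported as possibly secular.

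This takes a few sentences and no new data or patients. The plan should state the loss of precision in the adjusted model given in the working, so that a non-significant adjusted test is not read as evidence against moderation.
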